14.4 Planned PK analyses

Pharmacokinetic variables will be analyzed for all subjects in the PK-PPS.

Bimekizumab plasma concentrations will be summarized by PS0010/PS0011 treatment group at each scheduled visit. Descriptive statistics for the plasma concentrations at PS0010 Baseline will be presented followed by descriptive statistics for the observed, change from PS0010 Baseline, and change from PS0011 Baseline results for scheduled visits in PS0011. Summarizing in this manner based on the PS0010/PS0011 treatment group will allow for an evaluation of how changing doses (where applicable) impacted plasma concentrations relative to both the original (PS0010) Baseline as well as the new (PS0011) Baseline. For the descriptive statistics, geometric mean, geometric coefficient of variation, and 95% confidence interval for the geometric mean will be used instead of the arithmetic mean and standard deviation.

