14.5 Planned immunological analyses

Immunological variables will be analyzed for all subjects in the PK-PPS.

Anti-bimekizumab antibody data will be summarized by PS0010/PS0011 treatment group at each scheduled visit. The summary of anti-bimekizumab antibody levels will follow a similar approach to that used for the summary of bimekizumab plasma concentrations. Additional analyses related to antibody positivity will be performed and will be described in greater detail in the SAP.

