2.2.3 Immunological variable

The immunological variable is anti-bimekizumab antibody levels prior to and following study treatment.

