3.11 Changes to protocol-defined analyses

There have been no changes to the protocol-defined analyses.

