9.2 Immunogenicity

9.2.1 Anti-bimekizumab antibodies

Subjects with a positive on-treatment (i.e., excluding PS0010 Baseline) anti-BKZ antibody result in either PS0010 or PS0011 will be classified as anti-BKZ positive.

Anti-BKZ antibody status will be summarized for each PS0010/PS0011 treatment group at each scheduled PS0010 and PS0011 visit using the PK-PPS analysis set. The first occurrence of anti-BKZ antibody positivity will also be presented for each PS0010/PS0011 treatment group at each scheduled PS0010 and PS0011 visit.

The anti-BKZ antibody status will be determined for each visit where samples are taken for drug concentration means. The cut point for determining whether the anti-bimekizumab antibody level is sufficiently high to be considered anti-BKZ antibody positive is not yet known. However, this will be determined prior to the database lock of the PK and anti-BKZ antibody data.

A line plot of the percentage of anti-BKZ antibody positive subjects at each visit will be produced by PS0010/PS0011 treatment group. All individual subject-level anti-BKZ antibody results will be listed.

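### The SAP summarises anti-bimekizumab antibody status only, although the protocol asks for antibody levels by visit, and the departure is not declared

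*SAP*

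**What the plan says.** The two documents agree on the variable. SAP section 2.2.3, in the same words as protocol section 4.3, states: "The immunological variable is anti-bimekizumab antibody levels prior to and following study treatment".

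Protocol section 14.5 then makes three statements about its analysis:

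- The general requirement: "Anti-bimekizumab antibody data will be summarized by PS0010/PS0011 treatment group at each scheduled visit".
- How levels are to be handled: "The summary of anti-bimekizumab antibody levels will follow a similar approach to that used for the summary of bimekizumab plasma concentrations".
- What comes on top: "Additional analyses related to antibody positivity will be performed and will be described in greater detail in the SAP".

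The plasma-concentration approach that it points to is in protocol section 14.4. For each PS0010/PS0011 group, PS0010 Baseline statistics come first. Observed values and changes from both the PS0010 and the PS0011 Baseline then follow, visit by visit. The statistics are quantitative: "geometric mean, geometric coefficient of variation, and 95% confidence interval for the geometric mean will be used instead of the arithmetic mean and standard deviation".

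SAP section 9.2.1 plans the following: "Anti-BKZ antibody status will be summarized for each PS0010/PS0011 treatment group at each scheduled PS0010 and PS0011 visit using the PK-PPS analysis set". It continues: "The first occurrence of anti-BKZ antibody positivity will also be presented for each PS0010/PS0011 treatment group". It adds a line plot of the percentage positive by visit and a listing of individual antibody results. SAP section 3.11 says: "There have been no changes to the protocol-defined analyses".

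**The concern.** The protocol orders two things, a summary of levels and further work on positivity. The SAP carries out the second and leaves out the first, without saying so.

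Immunogenicity is one of the two objectives that both documents class as other. Status is a level cut at a threshold, so a stable result just above the cut point and a large, rising response are counted alike in every planned table.

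The design makes this distinction worth having. Some subjects move up in dose on entering PS0011 (64mg to 160mg, 160mg to 320mg) and others move down (480mg to 320mg). Protocol section 14.4 gives the effect of dose changes as the reason for showing change from two Baselines, and section 14.5 carries a similar approach over to antibody levels. A group-level shift in level after a dose change would not appear in any planned table or figure unless it also moved subjects across the cut point.

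**Working it through.** No formula applies; the check is a comparison of text.

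**1. What is the variable?** Level, in protocol section 4.3 and SAP section 2.2.3 alike.

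**2. Does the protocol require levels to be summarised, or only antibody data in some form?** Levels. "The summary of anti-bimekizumab antibody levels will follow a similar approach to that used for the summary of bimekizumab plasma concentrations" names the quantity and gives a model for summarising it. The positivity sentence in the same section opens with the word for extra work, so positivity supplements the level summary and does not stand in for it.

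**3. Which planned SAP outputs use antibody data, and in what form?**

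| SAP section | Output | Form used |
|---|---|---|
| 9.2.1 | By-visit table by PS0010/PS0011 group | Status |
| 9.2.1 | First occurrence of positivity by visit | Status |
| 9.2.1 | Line plot of percentage positive | Status |
| 4.7 | Subgroup for the secondary efficacy variables | Ever positive on treatment, yes/no |
| 8.2.1 | TEAEs by onset relative to antibody | Status |
| 9.2.1 | Listing of individual results | As reported |

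Five outputs summarise status. None summarises level or change in level. The sixth is a listing, which is not a summary by group and visit.

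**4. Does a level exist behind the status?** The SAP's text implies that it does: section 9.2.1 describes positivity as the antibody level being high enough to pass a cut point. Protocol section 11 speaks of determining the presence of antibodies and leaves details to a bioanalytical report. The documents do not state whether a numeric value is reported for every sample.

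**5. Is the departure declared?** No. SAP section 3.11 reports no changes.

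**6. What is the scope?** The missing summary covers all eight PS0010/PS0011 groups. Table 5-1 schedules nine antibody time points: Baseline, Weeks 4, 8, 12, 16, 28, 40 and 48/withdrawal, and the SFU visit.

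**The case against.** The strongest reply is that the information is not lost. SAP section 9.2.1 lists every individual antibody result, and SAP section 3.1 promises listings of documented and calculated data, giving change from Baseline as an example, by PS0010/PS0011 group. A rising value in one subject could be read there. This stands, and it rules out the stronger inference that the size of the response goes unexamined. Levels are listed but not summarised by group.

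A reader might also object that status tables rest on a cut point not known when the SAP was written. The documents do not support a complaint here. SAP section 9.2.1 says that the cut point will be fixed before lock of the PK and antibody data, and protocol section 11 requires the threshold before analysis.

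Multiplying the nine time points by up to 240 subjects, to count results reduced to yes or no, would mislead as well. It gives only a ceiling on samples. Withdrawals and the restriction to the PK-PPS lower it, and the individual results are still listed.

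Two further replies concern the assay and the wording. The documents never mention a titre, and they do not confirm that a usable number exists for each sample. This is a fair limit on the remedy, but if no number exists, SAP sections 2.2.3 and 3.11 are still inaccurate. Also, the protocol asks only for a similar approach to PK, which leaves the exact statistics open. That freedom covers how levels are summarised, not whether they are.

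Finally, the SAP does add useful status-based work: PS0010 visits, first positivity, TEAE timing and an efficacy subgroup. This is to its credit, but all of it uses status.

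**Conclusion.** The inconsistency is real. A by-visit summary of antibody level, ordered by protocol section 14.5 for the variable that both documents name, is absent from the SAP for all eight PS0010/PS0011 groups, and SAP section 3.11 wrongly reports no change. Following the SAP as written would leave a protocol-ordered summary out of the report.

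Its weight is moderate. Immunogenicity is not a primary or secondary objective, no inferential analysis is planned, and individual results will be listed. Neither the primary safety variable nor any efficacy summary is affected.

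The finding that 14.5 and 9.2.1 disagree rests on the text alone. The practical value of a level table rests on one assumption that the documents do not settle: that the assay reports a numeric level fit to summarise.

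**What to change.** Add to SAP section 9.2.1 a by-visit descriptive table of antibody level by PS0010/PS0011 group on the PK-PPS. It should show PS0010 Baseline, observed values, and change from the PS0010 and PS0011 Baselines, in line with protocol sections 14.4 and 14.5. Draft it from protocol section 14.4, because SAP section 9.1 shows change from the PS0011 Baseline only.

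State a rule for results below the assay limit or cut point. SAP section 9.1 already has such a rule for concentrations: half the lower level of quantification, with only the median, minimum and maximum shown unless at least two thirds of values are above that level. The SAP should say whether the same rule or another one applies to antibodies.

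If the assay gives no usable numeric level, record in SAP section 3.11 that status has replaced level, with the reason, and align SAP section 2.2.3.

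The cost is one more table and a rule for low values, or a few corrected sentences. SAP section 3.3 already maps antibody results from early withdrawal visits. The table may be sparse in small groups.

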10 EFFICACY ANALYSES

10.1 Statistical analysis of the efficacy variables

Efficacy variables will be analyzed for all subjects in the FAS.

Also, summary tables of each endpoint by visit and treatment will be provided.

Unless otherwise specified, summary tables for efficacy endpoints by PS0010/PS0011 treatment group will present data separately by responder status (defined as PS0010 Week 12 PASI90 response).

Efficacy endpoints will also be listed.

10.1.1 PASI score and response

10.1.1.1 Derivation of PASI score and response

PASI scoring of psoriatic plaques is based on three criteria: redness (R), thickness (T), and scaliness (S). Severity is rated for each index (R, S, T) on a 0-4 scale (0 for no involvement, up to 4 for very marked involvement). The body is divided into four areas comprising the head (h), upper extremities (u), trunk (t), and lower extremities (l). In each of these areas, the fraction of total surface area affected is graded on a 0-6 scale (0 for no involvement, up to 6 for 90%-100% involvement).

The various body regions are weighted to reflect their respective proportion of BSA. The composite PASI score is then calculated by multiplying the sum of the individual-severity scores for each area by the weighted area-of-involvement score for that respective area, and then summing the four resulting quantities. PASI is therefore calculated as (note that the R, T, and S scores are as follows: 0 = none, 1 = slight, 2 = moderate, 3 = marked, and 4 = very marked):

$$\begin{aligned} \text{PASI} = & (0.1 \times (R_h + T_h + S_h) \times A_h) + (0.2 \times (R_u + T_u + S_u) \times A_u) \\ & + (0.3 \times (R_t + T_t + S_t) \times A_t) \\ & + (0.4 \times (R_l + T_l + S_l) \times A_l) \end{aligned} \quad (14)$$

where

R_h, R_u, R_t, R_l = redness score of plaques on the head, upper extremities, trunk, and lower extremities, scored 0-4 respectively

T_h, T_u, T_t, T_l = thickness score of plaques on the head, upper extremities, trunk, and lower extremities, scored 0-4 respectively

S_h, S_u, S_t, S_l = scaliness score of plaques on the head, upper extremities, trunk, and lower extremities, scored 0-4 respectively

A_h, A_u, A_t, A_l = numerical value translation of % area of psoriatic involvement score for the head, upper extremities, trunk, and lower extremities respectively (where 0 = 0% [clear], 1 = >0% to <10%, 2 = 10% to <30%, 3 = 30% to <50%, 4 = 50% to <70%, 5 = 70% to <90%, and 6 = 90% to 100%).

The highest potential PASI score is 72 for severe disease and the lowest is 0 for no psoriasis lesions. PASI scores are treated as a continuous score, with 0.1 increments within these values. The percent improvement in PASI scores from Baseline will be computed as:

$$\begin{aligned} \text{Percent improvement in PASI} \\ = 100 \times \frac{\text{Baseline PASI} - \text{Post-Baseline PASI}}{\text{Baseline PASI}} \end{aligned} \quad (15)$$

If a subject has experienced an improvement, this measure will be positive. If a subject has experienced a worsening in their condition, this measure will be negative.

If a subject is missing one or two severity measurements for a certain region, the average of the remaining severity measurement(s) within that region will be utilized to substitute for the missing severity measurement(s) in that region. If the area of affected skin and/or all severity measurements for up to two regions are missing, then the missing $(R + T + S) \times A$ for a region will be substituted by the average of the available $(R + T + S) \times A$. Otherwise, the PASI will be set to missing.

A categorical variable, PASI90 response, is defined to be equal to 1 if the percentage improvement from Baseline in the PASI scores is 90% or greater and 0 if the percentage improvement from Baseline is less than 90%. This definition is introduced for the purpose of identifying subjects who respond to the treatment (1 = responder, 0 = non-responder). Similarly, the categorical efficacy variables PASI75 and PASI100 response are equal to 1 for subjects with improvements of 75% or greater and 100% from Baseline in PASI score respectively, and equal to 0 otherwise.

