12 ASSESSMENT OF EFFICACY

12.1 Psoriasis Area and Severity Index

The PASI is the most commonly used and validated assessment for grading the severity of psoriasis in clinical studies (Feldman, 2004). The PASI quantifies the severity and extent of the disease and weighs these with the percentage of BSA involvement.

The degree of involvement is estimated across 4 body areas; head, upper limbs, trunk, and lower limbs and then transferred into a grade ([Table 12-1](#)).

The Investigator assesses the average redness, thickness, and scaliness of lesions in each body area (each on a 5-point scale); 0=none, 1=slight, 2=moderate, 3=marked, and 4=very marked.

The PASI score ranges from 0 to 72 with a higher score indicating increased disease severity.

Table 12–1: Body areas for calculation of percent BSA for PASI

Body area	Details of area	BSA	Degree of involvement of body area ^a
Head	Face, back of head	10%	0 to 6
Upper limbs	Left, right, upper lower, flexor surface, extensor surface	20%	0 to 6
Trunk	Front, back, groin	30%	0 to 6
Lower limbs	Left, right, upper lower, flexor surface, extensor surface, including buttocks	40%	0 to 6
Total		100%	

BSA=body surface area; PASI=Psoriasis Area and Severity Index

^a Where 0=none; 1=1% to <10% affected, 2=10% to <30% affected, 3=30% to <50% affected, 4=50% to <70% affected, 5=70% to <90% affected, 6=90% to 100% affected.

The PASI50, PASI75, PASI90, and PASI100 responses are based on at least 50%, 75%, 90%, and 100% improvement in the PASI score. The improvement will be based on changes from the PASI score at the Baseline of PS0010.

The PASI will be completed at the visits specified in [Table 5–1](#).

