4.2.2 Handling missing data for the efficacy analyses

For the planned efficacy analysis, missing responder data will be imputed using non-responder imputation (NRI). That is, subjects that discontinue study medication early or who have missing data at a given time point will be counted as non-responders. Summaries based on observed case data will also be prepared.

Continuous efficacy variables will be imputed using multiple imputation (MI) via the Markov-Chain Monte Carlo (MCMC) method. Summaries based on observed case data will also be prepared.

The MI procedure for continuous efficacy variables (based on MCMC) will be applied as follows:

1. Create a dataset, one for each treatment group, of subjects with observed values and those needing estimation by multiple imputation. The missing values in each dataset will be filled in using the MCMC method with a total of 100 sets of imputations being performed. Values at Baseline and at each post-Baseline visit will be included in the imputation model in chronological order with prior biologic exposure and region as factors. The resulting datasets for each treatment arm will be combined into one complete dataset based on each of the 100 imputations.

Note: The imputation model based on the MCMC method will only allow continuous variables in the imputation model. Therefore, prior biologic exposure and region will be re-coded as indicator variables (with values of 0 or 1 for each level of the variable). In order to achieve model convergence, prior biological exposure may be dropped from the model, if convergence is still not obtained then region may also be dropped from the model.

2. The relevant change from Baseline (or percent change from Baseline) values will then be derived based on the imputed datasets and will be summarized by imputation.
3. The summary statistics from each of the 100 imputed datasets will be combined for the calculation of means and standard deviations using Rubin's rules, which account for the uncertainty associated with the imputed values (Rubin, 1987). This will be done using SAS PROC MIANALYZE. For calculation of other descriptive statistics such as the median, min and max, Rubin's rules do not apply. Multiple imputation estimates will be computed by simply averaging the estimates from the $m = 1, \dots, M$ independent repetitions of the imputation algorithm:

$$\bar{\theta} = \frac{1}{M} \sum_{m=1}^M \hat{\theta}_m$$

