10.1.7 PSSI

10.1.7.1 Derivation of PSSI

The PSSI considers both the extent of the scalp area of involvement and the severity based on the scoring scales outlined in [Table 10-4](#) and [Table 10-5](#).

The assessment considers erythema, induration and desquamation on the scalp. For each of these three elements, the scores of the area and severity are multiplied. Then, the score from each element is totaled to obtain the PSSI score. As with the PASI, the PSSI score ranges from 0 to 72 with a higher score indicating increased scalp disease severity.

If a subject is missing one severity measurement, the average of the remaining severity measurements will be utilized to substitute for the missing severity measurement. If the area of affected skin is missing or if two or more severity measurements are missing, then the PSSI score will be set to missing.

Table 10–4: PSSI assessment of extent of scalp psoriasis

Score	Definition
1	<10%
2	10 – 29%
3	30 – 49%
4	50 – 69%
5	70 – 89%
6	90 – 100%

Table 10–5: PSSI assessment of clinical symptoms

Score	Definition
0	Absent
1	Slight
2	Moderate
3	Severe
4	Severest possible

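### The PASI and PSSI missing-item rules impute or discard scores that the recorded items already fix at 0

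*SAP*

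**What the plan says.** SAP 10.1.1.1 (equation 14) weights the products (R + T + S) × A of head, upper limbs, trunk and lower limbs by 0.1, 0.2, 0.3 and 0.4. The area grade A is coded "where 0 = 0% [clear], 1 = >0% to <10"%, and so on up to 6.

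Blanks are then handled in three steps:

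- One or two severities blank in a region: "the average of the remaining severity measurement(s) within that region will be utilized to substitute for the missing severity measurement(s) in that region".
- Wider gaps in at most two regions, a case the SAP introduces with "If the area of affected skin and/or all severity measurements for up to two regions are missing": the regional product is replaced by the average of the available products.
- Anything beyond that: "Otherwise, the PASI will be set to missing".

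For responder variables, SAP 4.2.2 provides that subjects "who have missing data at a given time point will be counted as non-responders", and SAP 10.1.1.2 applies this to PASI75, PASI90 and PASI100.

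For the scalp, SAP 10.1.7.1 multiplies extent by each of three severities and adds the results. "If the area of affected skin is missing or if two or more severity measurements are missing", PSSI is missing. The extent codes in Table 10-4 run from 1 to 6. Missing PSSI is filled by multiple imputation (SAP 10.1.7.2), or by LOCF if the imputation model does not converge (SAP 4.2.2).

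**The concern.** The PASI rule is triggered by a missing component, not by an undetermined product. Two patterns leave a component blank while the product is certain: A = 0 with R, T and S all blank, and A blank with R = T = S = 0. In both the product is 0 whatever the blank would have held. The rule nevertheless fills in the other regions' average or, from three such regions, drops the whole score.

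Elsewhere the SAP does deal with structural zeros. An unaffected nail adds nothing to mNAPSI (10.1.5.1), and an answer of not relevant to DLQI question 7 scores 0 (10.1.4.1). PASI and PSSI have no counterpart.

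Blanks in clear regions are plausible, because Protocol 12.1 says "The Investigator assesses the average redness, thickness, and scaliness of lesions in each body area" and a clear region has no lesions to rate.

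At stake are PASI90, a secondary efficacy variable, together with PASI75, PASI100, the absolute PASI thresholds and the PASI change scores. For PSSI, a clear scalp would leave the observed-case summaries and be replaced by an imputed value.

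**Working it through.** **The plan's own range.** "The highest potential PASI score is 72 for severe disease and the lowest is 0 for no psoriasis lesions". Equation 14 reproduces it: (0.1 + 0.2 + 0.3 + 0.4) × 12 × 6 = 72, and 0 when every product is 0. The PSSI maximum also checks: 3 × 4 × 6 = 72.

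**Inputs.** The weights, area codes and blank rules come from SAP 10.1.1.1. PS0010 Baseline PASI is an assumption: 20, with a range of 12 to 40. The SAP supplies only a subgroup cut at 20 (section 4.7).

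**Example.** Arms R = T = S = 2 and A = 1, so the product is 6. The other regions have A = 0. Head severities are entered as 0; trunk and leg severities are blank.

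- True PASI = 0.2 × 6 = 1.2.
- Under the rule, the average available product is (0 + 6)/2 = 3, so PASI = 0.1 × 0 + 0.2 × 6 + 0.3 × 3 + 0.4 × 3 = 3.3.
- The result is the same if trunk and leg areas are blank and their severities are all 0.

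Improvement = 100 × (Baseline − PASI)/Baseline:

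| Assumed Baseline | True (1.2) | Rule (3.3) | PASI90 under the rule |
|---|---|---|---|
| 12 | 90.0% | 72.5% | lost (PASI75 too) |
| 15 | 92.0% | 78.0% | lost |
| 20 | 94.0% | 83.5% | lost |
| 30 | 96.0% | 89.0% | lost |
| 40 | 97.0% | 91.8% | kept |

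The absolute thresholds in SAP 10.1.1.2 move as well: 1.2 meets ≤2 and ≤3, and 3.3 meets neither.

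**Variations, same arms.**

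- Only the legs blank: average (0 + 6 + 0)/3 = 2, PASI = 1.2 + 0.4 × 2 = 2.0. PASI90 is lost at Baselines 12 (83.3%) and 15 (86.7%) and kept from 20 (90.0%) upward.
- Head, trunk and legs blank: PASI missing, hence non-response, against a true 1.2.
- One or two leg severities blank with A = 0: the filled-in value is multiplied by 0, so PASI stays at 1.2 and no harm is done.

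**Fully clear subject.** With one or two regions blank, the average of the others is 0 and PASI is correctly 0. With three or four blank, PASI is missing and a true PASI100 responder becomes a non-responder on all three responder variables.

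**Baseline.** Products: upper limbs 20, trunk 20, lower limbs 25; head A = 0 with severities blank.

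- True Baseline = 0.2 × 20 + 0.3 × 20 + 0.4 × 25 = 20.
- The rule adds 0.1 × 65/3 = 2.17, giving 22.17.
- A follow-up PASI of 2.2 is then a 90.1% improvement instead of 89.0%, and PASI90 is gained.

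**PSSI.** With severities 0, 0, 0 and extent blank, each product is 0, so PSSI = 0. The rule makes it missing.

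**The case against.** Severity has a defined zero. Protocol 12.1 and SAP 10.1.1.1 both give 0 as the code for no involvement, so a clear region can be completed in full. Nothing says sites skip those fields, and Protocol 13.3.2 provides computerized checks and manual review. The eCRF and its completion guidelines are not among the documents. This stands: the frequency is unknown and may be nil.

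The substitution is worded as applying to a missing product, so an analyst could treat a product with A = 0 as known. That is a sensible reading, but the triggering condition names the components, and a programmer following the text would impute.

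No inferential analysis is planned (Protocol 14.2), so no test decision depends on this, and observed-case summaries accompany the imputed ones. The observed-case tables do not repair the error, however. They would carry the same 3.3 and would omit the scores set to missing.

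PSSI extent code 1 is labelled <10%, which can be read to cover 0%. A clear scalp could then be entered as extent 1 with severities 0, giving PSSI = 0. That is fair, though the PASI scale separates 0% from code 1 and the PSSI scale has no explicit 0.

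**Conclusion.** The point holds in limited form. Read literally, SAP 10.1.1.1 replaces or discards a regional product known to be 0 when the area is 0 and all three severities are blank, or when the area is blank and all severities are 0. In the example it raises PASI from 1.2 to 3.3 and loses PASI90 at assumed Baselines of 12, 15, 20 and 30, but not at 40. SAP 10.1.7.1 discards a known PSSI of 0 when extent is blank and all severities are 0.

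A reader might infer more than the documents support:

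- *Any blank in a clear region does damage.* It does not: one or two blank severities are harmless, and a fully clear subject is affected only from three blank regions.
- *The bias always runs against response.* At follow-up the average can only raise PASI, but at PS0010 Baseline the same rule favours response.
- *Clear scalps become non-responders.* No PSSI responder variable is defined; missing PSSI goes to MI or LOCF.
- *Treatment assignment is affected.* Assignment runs through the IXRS (Protocol 7.10), and the SAP does not say its item rule governs that step.

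The size rests on the assumed Baselines and on such blanks occurring at all. If zeros are always entered, nothing changes.

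**What to change.** In SAP 10.1.1.1, before the missing-item sentences, add: *If the area score of a region is 0, or all three severity scores are 0, the regional product is 0 and is not treated as missing.* State that it applies at Baseline and at post-Baseline visits.

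In SAP 10.1.7.1, add: *If all three severity scores are 0, PSSI = 0 even if extent is missing.* If an extent code 0 for an uninvolved scalp is introduced, add that PSSI = 0 when that code is recorded.

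The existing rules then apply only where the product is genuinely unknown. The cost is two sentences and a small change to the derivation code. Results do not change if zeros were always entered. A count of region-visits showing either pattern would settle whether the point matters in practice.
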